 335 receiving BL but not for the amber PL
 336 group. Greater FA is generally considered
 337 to signify better white matter health. These
 338 preliminary data raise the intriguing possibility that improvement in sleep during the six-week treatment
 339 period with BL may lead to an accelerated re-myelination process relative to those in the PL group. We
 340 believe further research into this intriguing and potentially important possibility and its relation to PTSD
 341 symptom change is warranted.

[figure not shown]

Figure 9. The blue light (n = 7) condition showed significantly greater increases in resting state functional connectivity between the hippocampus and other posterior sensory regions, and increased functional connectivity between the prefrontal cortex and a number of other higher order association regions compared to the amber light placebo group (n = 5), which showed greater post-treatment functional connectivity of the visceral and bodily awareness regions.

342 **Summary.** Our preliminary findings clearly demonstrate that the methods proposed herein are
 343 feasible and that our team can effectively collect, process, and analyze the data, thereby accomplishing the
 344 aims of the study. We have now implemented this paradigm with over 30 brain injured participants, and
 345 all were able to complete the study procedures without difficulty. Furthermore, the case findings we
 346 highlight also provide limited but compelling evidence that the BLT program was associated with
 347 improvement in symptoms, neuropsychological status, and neurocircuitry changes in the hypothesized
 348 direction. Thus, the preliminary data suggest that the protocol we propose is feasible and shows
 349 significant promise for improving sleep and brain functioning.

350

 351 **B. SPECIFIC AIMS/HYPOTHESES**

352 **Project Overview.** Combat veterans and other individuals with PTSD will complete two comprehensive
 353 sessions including neurobehavioral assessments, repeated polysomnographic sleep studies, and
 354 neuroimaging sessions (functional MRI, structural MRI, and proton spectroscopy) separated by 6 weeks
 355 of actigraphically monitored at-home treatment. During the intervening 6 weeks, participants will be
 356 randomly assigned to receive 30 minutes of daily morning blue light therapy (BL) or an amber light
 357 placebo treatment (PL). Sleep quality and quantity will be measured using subjective reports, objective

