**FORM: Application for Human Research**

| NUMBER | FORM DATE | PAGE |
|--------|-----------|----------|
| F200 | 02/2014 | 15 of 44 |

402 **3d:** Relative to PL, six weeks of BL will be associated with increased levels of GABA and
403 reduced glutamate in the amygdala-hippocampal complex and anterior cingulate gyrus as measured by
404 proton magnetic resonance spectroscopy (1H MRS).

405 **3e:** Relative to PL, six weeks of BL will produce increased levels of N-acetyl-aspartate
406 (NAA), choline (Cho), and reduced phosphocreatine (Cr) within the amygdala-hippocampal complex and
407 anterior cingulate gyrus.

408 **AIM 4:** The fourth Aim is to demonstrate whether changes in subjective and objective measures
409 of sleep are associated with changes in symptom severity, cognitive functioning, brain activation, and
410 neurochemistry. Regardless of the success of the light therapy approach outcome in Aim 1, the available
411 data will provide some of the first longitudinal data examining changes in sleep patterns over time in
412 individuals with PTSD and their correlation with these other metrics. Thus, useful data will be acquired
413 even if the primary hypothesis of Aim 1 is not supported.

414 **Hypothesis 4: Improvements in sleep noted in Hypothesis 1, will be linearly correlated with
415 improvements in cognitive and symptom functioning in Hypothesis 2 and structural and functional
416 brain changes in Hypothesis 3.**

417 **4a:** Changes in sleep parameters identified in Hypothesis 1 will correlate with
418 improvements in memory, executive functioning, and neuropsychological performance on neurocognitive
419 measures described in Hypothesis 2.

420 **4b:** Changes in sleep parameters identified in Hypothesis 1 will correlate with changes in
421 neurochemistry as outlined in Hypothesis 3d and 3e above.

423 **2) Lay Summary (approximately 400 words)**

424 Sleep disturbance is nearly ubiquitous among individuals suffering from PTSD and is a major problem
425 among service members returning from combat deployments. Recent evidence suggests that adequate
426 restorative sleep may a crucial component in the ability to generalize fear extinction learning, and
427 ultimately may be a key feature in the process of recovery from PTSD. The proposed study aims to test a
428 novel, inexpensive, and easy to use non-pharmacologic approach to improving sleep among service

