**FORM: Application for Human Research**

| NUMBER | FORM DATE | PAGE |
|--------|-----------|----------|
| F200 | 02/2014 | 26 of 44 |

841 palm-recorded skin conductance response (SCR), a reliable index of sympathetic activation. Participants
842 will be conditioned and undergo extinction prior to entry into the scanner. During scanning, participants
843 will again be confronted with the previously extinguished stimuli to evaluate extinction recall, a hallmark
844 deficit of PTSD. It is expected that improved sleep due to the BL condition will lead to improved
845 generalization of the extinction response and extinction recall.

846 **Modified Sleep Latency Test (MSLT):** Participants will undergo 3 MSLT procedures with
847 polysomnographic (PSG) recording over the course of the assessment day. A trained technician will fit
848 each participant with a standard electrode montage for PSG recording. Standard PSG will be recorded
849 using the Polysmith 11.0 system that is installed in our sleep laboratory facilities. During each MSLT, the
850 participant will be given up to 20 minutes to fall asleep in a private, darkened, sound-attenuated bedroom.
851 PSG recordings will be scored by a trained technician to determine the latency to fall sleep. The mean
852 latency to sleep is taken as an indication of objective sleepiness.

853 **Psychomotor Vigilance Test (PVT):** The PVT is a 10-minute computerized measure of
854 sustained attention and psychomotor vigilance that has been shown to be exquisitely sensitive to sleep
855 deprivation. The PVT currently serves as the “gold standard” for assessing degradation in alertness and
856 vigilance following sleep loss.

857 **Functional Neuroimaging:** Subjects will be screened for any contraindications to MRI and magnetic
858 materials. The investigator or MRI Technologist will explain the MRI system and the scan that they are
859 about to take part in. The subject will be asked to lie down on the scanner bed. Some part of the subject's
860 body may be covered or enclosed within an FDA or UA HSPP approved MRI coil. The subject may be
861 asked to interact with a peripheral system such as a button, joystick, or TV system before, during, or after
862 the scan.

863 Blood Oxygen Level Dependent (BOLD) functional magnetic resonance imaging (fMRI) will
864 be collected at the University of Arizona Translational Bioimaging Resource. The MRI hardware and

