**FORM: Application for Human Research**

| NUMBER | FORM DATE | PAGE |
|--------|-----------|----------|
| F200 | 02/2014 | 31 of 44 |

1039 and gender. Randomization will consist of permuted blocks to achieve balance over time. Repeated
1040 measures analysis of variance (ANOVA) and linear mixed-model approaches will be used for the primary
1041 analyses examining the efficacy of light treatment condition on measures of mood and sleep. Between
1042 group factors will correspond to the two light conditions (BL vs PL) and will control for any baseline
1043 differences in demographic variables and severity scores as appropriate. Based on specific hypotheses,
1044 separate ANOVAs will be performed for each type of dependent variable (e.g., subjective sleep scores,
1045 CAPS-2 symptom scores, mood scores, MRS metabolites). The relationship between these change
1046 indices and sleep variables will be analyzed using correlation and linear regression models in SPSS. Tests
1047 for normality will be conducted for all variables. In the case on non-normality, appropriate data
1048 transformation or non-parametric techniques will be employed (e.g., Kruskal-Wallis or Friedman tests for
1049 ANOVA; Mann-Whitney U or Wilcoxon for 2-group comparisons). Inflation of Type I error will be
1050 controlled first through the use of planned comparisons based on the hypotheses and the use of protected
1051 omnibus F-tests. Post-hoc analyses will be undertaken with protected comparisons (e.g., Tukey) or
1052 Bonferroni adjustment. Functional MRI data will be analyzed using statistical parametric mapping
1053 (SPM8) software, implementing the general linear model to compare pre- to post-therapy changes in
1054 functional responses between the active and placebo groups and across diagnostic groups, and sleep
1055 variables will be tested as covariates in the models. Finally, proton spectroscopy data for each of the
1056 metabolites will be quantified and compared for pre- to post-therapy changes in metabolite concentrations
1057 between the active and placebo treatment groups and across diagnostic groups. Type I error during
1058 neuroimaging will be controlled via whole brain False Discovery Rate (FDR) correction or small volume
1059 corrections using Family Wise Error (FWE) rate within *a priori* specified regions of interest. To handle
1060 missing data, we will first determine the potential cause of the data loss. Statistically, missing data can be

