1061 considered as falling into three types: 1) missing completely at random, 2) missing at random, or 3)
1062 missing not at random. The type of missing data will dictate the approach. Assuming type 1, and that the
1063 number of missing values is low, we will use a standard listwise deletion procedure. However, assuming
1064 that a larger number of values is missing, and data are not missing completely at random, we will be able
1065 to apply missing data imputation methods.

1066 **Power Analysis:** A power analysis based on a proposed sample size of 90 subjects suggested that
1067 with an omnibus 2 between-groups (BL vs. PL) x 2 within-subjects (pre- vs post-treatment) mixed design,
1068 assuming a moderate effect size ($f = .25$), and $\alpha = .05$, there should provide be adequate power to detect
1069 most effects. First, the primary hypotheses of the study focus on interaction effects across groups (i.e.,
1070 treatment x session interactions), which will have exceptional power ($1-\beta = 0.99$) to detect a moderate
1071 effect size at $\alpha = .05$ (see Figure 18A). Paired comparisons within each group of will also have excellent
1072 power of .91 to detect moderate effect size changes ($d = .50$), with 2-tailed tests (see Figure 18B).
1073 Without regard to group differences, a sample size of 90 would yield power = 0.84 to detect a moderate
1074 linear association (i.e., $r \geq .30$) between a predictor variable (e.g., average sleep; change in sleep
1075 parameters, PTSD symptom severity; neurocognitive performance; etc.) and an outcome variable (e.g.,
1076 fMRI signal intensity changes; spectroscopic metabolite changes; etc.), with a two-tailed test at $\alpha = .05$
1077 (see Figure 16). Thus, the proposed sample size of $n = 45$ per group appears to provide adequate power
1078 for testing the major hypotheses of the proposed study.

FORM: Application for Human Research

| NUMBER | FORM DATE | PAGE |
|---------------|------------------|-------------|
| F200 | 02/2014 | 32 of 44 |

1079 **Functional Image Pre-Processing:** Functional neuroimaging data will be preprocessed in SPM8
1080 [123]. Following standard algorithms, functional images will be slice-time corrected, co-registered to
1081 their anatomical T1-weighted images, realigned, unwarped to correct for field inhomogeneity, normalized
1082 to the standard three-dimensional space of the Montreal Neurological Institute (MNI), spatially smoothed

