**FORM: Application for Human Research**

| NUMBER | FORM DATE | PAGE |
|--------|-----------|----------|
| F200 | 02/2014 | 33 of 44 |

1120 subgenual and rostral ACC, VMPFC, and amygdala. Data will be analyzed at an FDR corrected
1121 significance level of $p < 0.05$.

1122 **MRS Analyses:** The goal will be to determine whether BL treatment is more effective than PL at
1123 altering brain metabolites that are associated with alertness, cognitive processing, and inhibitory capacity.
1124 All MRS processing will be carried-out in a fully automated fashion using methods previously published
1125 by our group [127]. Metabolite ratios will be derived as a ratio of each raw metabolite integral to the total
1126 sum of the creatine and phosphocreatine integrals, and will be T1-corrected using values previously
1127 reported in the literature. Our primary endpoints of interest are Glu (excitatory neurotransmitter), GABA
1128 (inhibitory neurotransmitter), and NAA (marker of neuronal energy production). Standard linear and
1129 mixed model approaches will be employed for comparing metabolite ratios between the active BL and
1130 placebo light conditions within the dorsal ACC and amygdala-hippocampal complex. As described
1131 above, all analyses will be undertaken with $\alpha = .05$, employing corrections for multiple comparisons (e.g.,
1132 Tukey post-hoc corrections; Bonferroni corrections) as appropriate. We expect that the active BL
1133 condition will lead to increased levels of GABA, N-acetyl-aspartate (NAA), and choline (Cho), and
1134 reduced glutamate and phosphocreatine (Cr) in the amygdala-hippocampal complex and anterior cingulate
1135 gyrus compared to the PL condition. Furthermore, it is expected that these changes will be linearly
1136 related to changes in sleep parameters and cognitive/symptom score changes from pre- to post-
1137 assessment.

1138 8) Risks to subjects

1139 Participation in this study may involve some risks or discomforts, which are described below.
1140

1141 During the study visits, subjects may be asked some questions during the brief clinical interview
1142 and on the questionnaires that deal with personal or emotional matters. These questions might cause
1143 psychological discomfort. Subjects may refuse to answer any questions that make them uncomfortable. If
1144 they reveal during these sessions that they are currently or have recently had thoughts of self-harm or

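### The Hypothesis 4 sleep-change analyses name no treatment-arm term for behavioural, symptom and spectroscopy outcomes, so a pooled correlation cannot separate a within-arm link from the light shifting both variables

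*Combined protocol and SAP*

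**What the plan says.** The Global Statistical Analysis Approach (Section 3, D. Data Analysis) names blue versus placebo light as the between-group factor for the ANOVA and mixed-model comparisons of treatment. For the link to sleep it changes method: the relationship between change "indices and sleep variables will be analyzed using correlation and linear regression models in SPSS". No arm term, arm-by-sleep interaction, within-arm analysis or mediation model is named for that step.

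The other relevant places are these:

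- **Power Analysis.** "Without regard to group differences, a sample size of 90 would yield power = 0.84 to detect a moderate" linear association, with r of .30 or more and a two-tailed test at .05. The sentence is generic and also covers fMRI outcomes.
- **MRS Analyses.** Metabolite ratios are compared between arms. Separately, the metabolite changes are expected to be linearly "related to changes in sleep parameters and cognitive/symptom score changes from pre- to post" assessment, and no model is given for that link.
- **B. Specific Aims, Hypotheses 4a and 4b.** "Changes in sleep parameters identified in Hypothesis 1 will correlate with" neurocognitive improvement and with neurochemical change. The wording is associational.
- **Hypotheses 1, 2, 3d and 3e.** Blue light is predicted to shift sleep, cognition and symptoms, and metabolites, relative to amber light.
- **fMRI.** The general linear model compares pre-to-post change between arms, and sleep "variables will be tested as covariates in the models". Arm and sleep therefore appear to sit in one model, so fMRI is outside this point.

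**The concern.** If blue light improves sleep and also improves an outcome, participants in the blue arm tend to be high on both change scores and those in the amber arm low on both. Pooling the arms then produces a correlation even if, within each arm, the people whose sleep improved more did no better than the rest. The better the light works, the less the pooled figure says about sleep itself.

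The plan has a pathway through sleep in view. In the Fear Conditioning Paradigm text, "It is expected that improved sleep due to the BL condition will lead to improved" extinction generalisation and recall. In the pilot imaging, which came from concussion patients, an arm-level white-matter difference is read, with hedging, as a possible consequence of better sleep: the "preliminary data raise the intriguing possibility that improvement in sleep during the six-week treatment" period may have sped up re-myelination. The Spectroscopic Neuroimaging text speaks of identifying a potential mechanism, on the assumption that better sleep improves emotional functioning.

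No passage says the Hypothesis 4 correlations will be used to infer such a pathway. The risk is one of reporting: a significant pooled correlation could be presented as sleep change tracking improvement when it reflects only the shared arm shift.

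**Working it through.** **Inputs from the documents.** N = 90, 45 per arm (General Procedure); r = .30, two-sided .05, power .84 for the association; f = .25 and power .99 for the treatment-by-session interaction (Power Analysis).

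**Assumed.** The size of the treatment effect on change scores. Write d1 (sleep) and d2 (outcome) for the blue-minus-amber difference in mean change, in within-arm SDs of change, signed so that positive is improvement.

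**1. The plan's own figure.** Noncentral t with ncp = r√N/√(1 − r²) = .30 × √90/√.91 = 2.98 on 88 df gives power .839. The Fisher z version, Φ(atanh(.30) × √87 − 1.96), gives .823. The stated .84 is the power of a single pooled correlation on 90 people.

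**2. Expected pooled correlation.** With 1:1 allocation and within-arm correlation r:

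pooled r = (r + d1·d2/4) / √[(1 + d1²/4)(1 + d2²/4)]

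- r = 0, d = (.5, .5): .0625/1.0625 = .06
- r = 0, d = (.9, .9): .2025/1.2025 = .17
- r = .30, d = (.5, .5): .3625/1.0625 = .34
- r = .30, d = (.9, .9): .5025/1.2025 = .42

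**3. How often the test is significant with no within-arm link.** Simulation of 200,000 trials per row: bivariate normal change scores, 45 per arm, within-arm SD 1, two-sided .05. The pooled test has 88 df and the arm-adjusted test 87.

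| (d1, d2) | Pooled | Arm in model |
|---|---|---|
| (0, 0) | .050 | .050 |
| (.5, 0) | .050 | .050 |
| (.9, 0) | .050 | .050 |
| (.3, .3) | .055 | .050 |
| (.5, .3) | .063 | .049 |
| (.5, .5) | .085 | .051 |
| (.55, .55) | .100 | .049 |
| (.9, .3) | .089 | .050 |
| (.9, .5) | .154 | .050 |
| (.71, .71) | .185 | .050 |
| (.9, .9) | .361 | .049 |
| (1, 1) | .485 | .049 |

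**4. Which d is plausible.** The documents do not say. A two-sample t test on change scores with 45 per arm has power .65 at d = .5 and .91 at d = .71; the stated .99 needs d of about .91. On the repeated-measures reading, f = .25 means d = .71 if the pre-post correlation is 0 and d = 1.0 if it is .5. Both correlations are assumptions.

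**5. Power for a true within-arm r of .30.**

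| Scenario | Pooled | Arm in model |
|---|---|---|
| No treatment effect | .827 | .823 |
| Sleep only, d = .5 | .803 | .823 |
| Sleep only, d = .9 | .749 | .823 |
| Fully through sleep, sleep d = .5 | .849 | .823 |
| Fully through sleep, sleep d = .71 | .869 | .823 |
| Fully through sleep, sleep d = .9 | .888 | .822 |
| Fully through sleep, sleep d = 1.0 | .900 | .823 |

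In the last four rows the outcome effect is .30 × sleep d.

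**The case against.** The strongest reply is that the planned test answers the stated question. Hypothesis 4 says that improvements will be linearly correlated, and a pooled correlation tests exactly that. The percentages above are then not false-positive rates for Hypothesis 4: at (.9, .9) the marginal correlation really is about .17, and 36% is the power to find it. They are error rates only against a within-arm null that the plan never states. This stands, and it is why the point concerns interpretation and does not make the test invalid.

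Second, the omission is silence. Linear regression can carry an arm term, and the power sentence sizes an association without requiring pooling. That is also true, but nothing in the text commits the analyst to including arm.

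Third, the excess is small unless the light moves both variables by more than about half an SD, and it vanishes if the light moves only one. This too stands.

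Fourth, adjustment may deliver less than it seems to. If the light's effect varies between people, for example through adherence, it still moves both variables together inside the blue arm. Suppose the person-level effect is shared by both variables, has an SD half its mean, and there is no direct sleep-outcome link. Arm-adjusted rejection is then about 6%, 8% and 14% at d = .5, .71 and .9, against 13%, 33% and about 61% pooled. That scenario creates a real within-arm correlation, so it does not contradict the 5% figure. It does show that adjusting for arm removes one explanation and does not establish causation, since sleep change is not randomised within arm.

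**Conclusion.** The concern holds as a recommended improvement to a secondary, associational analysis. For behavioural, symptom and spectroscopy outcomes the plan names no arm term for the sleep-change links, while predicting that treatment shifts both sides.

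The size is conditional. With equal effects on both variables and no within-arm link, the chance of a significant pooled correlation reaches 10% at about d = .55. It lies between 18% and 49% if both variables move by the amounts implied by f = .25 under an assumed pre-post correlation of 0 to .5. These figures assume normal change scores, a constant treatment effect and complete data on 90 participants.

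The conclusions on treatment efficacy, which rest on the treatment-by-session interaction, do not change.

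**What to change.** For the behavioural, symptom and spectroscopy outcomes, specify a regression of outcome change on sleep change with treatment arm in the model. Report the pooled correlation beside it, labelled as a marginal association. Base any statement that sleep change tracks improvement on the arm-adjusted estimate, and say that it does not by itself show mediation. An arm-by-sleep-change term can be added as a check. Confirm in the text that the fMRI models hold arm and the sleep covariates together.

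The cost is one degree of freedom and a variable already in hand. The adjusted test gains power over the pooled one if treatment moves only sleep. It gives up .03 to .08 if the effect is carried wholly through sleep, as the plan expects. Keeping the pooled figure alongside limits that loss. Splitting the sample into separate within-arm correlations is not a good substitute: with 45 per arm, power for r = .30 is only .54.

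### The plan claims control of Type I error, but its methods do not work across outcomes, no primary outcome is fixed, and the task-fMRI correction rules contradict each other

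*Combined protocol and SAP*

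**What the plan says.** All places are in Section 3 of the combined protocol and SAP.

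- **Global Statistical Analysis Approach (part D).** Type I inflation is to be "controlled first through the use of planned comparisons based on the hypotheses and the use of protected" "omnibus F-tests. Post-hoc analyses will be undertaken with protected comparisons (e.g., Tukey) or" Bonferroni adjustment. The same paragraph says that "separate ANOVAs will be performed for each type of dependent variable (e.g., subjective sleep scores", with CAPS, mood and MRS measures as the other examples. It ties the label primary to "analyses examining the efficacy of light treatment condition on measures of mood and sleep". For neuroimaging it sets FDR for the whole brain, or FWE within small volumes.
- **Power Analysis.** Power is worked out "with an omnibus 2 between-groups (BL vs. PL) x 2 within-subjects (pre- vs post-treatment) mixed design" at f = .25, N = 90 and alpha .05. It adds: "First, the primary hypotheses of the study focus on interaction effects across groups". Those hypotheses are plural and not listed.
- **MRS Analyses.** "Our primary endpoints of interest are Glu (excitatory neurotransmitter), GABA" and NAA, compared between the active and "placebo light conditions within the dorsal ACC and amygdala-hippocampal complex". Alpha is .05, with Tukey or Bonferroni where judged appropriate.
- **Lay Summary (item 2).** The primary outcome measures are PTSD symptoms together with imaging of brain structure, function, connectivity and neurochemistry.
- **FMRI Statistical Analysis.** The ROI analyses use small-volume FDR. The whole-brain exploratory analyses use FWE.

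**The concern.** The plan makes a positive statement that error inflation is controlled. For the treatment comparison in a two-arm, two-session design, the tools it relies on first adjust nothing across outcomes. The one tool that could do so, Bonferroni, is tied to post-hoc use or to discretion, with no list of tests to divide alpha over.

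The label primary also sits on different outcomes in different places, so nothing in these documents fixes which result confirms the trial or at what threshold. Sleep, mood, PTSD symptoms, imaging or metabolites could each be presented as the primary finding once results are known. For task fMRI, the same ROI or whole-brain result could pass under one part of the plan and fail under another.

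**Working it through.** **Step 1: the plan's own power figure.** Inputs from Power Analysis: f = .25, N = 90, two sessions, alpha .05. The pre-post correlation ρ is not given and is assumed here.

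λ = f² × N × 2 / (1 − ρ) = .0625 × 90 × 2 / (1 − ρ) = 11.25 / (1 − ρ), with 1 and 88 df.

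| ρ | λ | Power |
|---|---|---|
| 0 | 11.25 | .913 |
| .3 | 16.07 | .978 |
| .4 | 18.75 | .990 |
| .5 | 22.50 | .997 |

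The stated .99 is reproduced at ρ = .4. It is a correct figure for one test at .05, with no allowance for more than one primary hypothesis.

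**Step 2: what protected F and Tukey add.** With two arms and two sessions the treatment-by-session F has (2 − 1)(2 − 1) = 1 numerator df. It therefore tests a single contrast, the arm difference in change. Critical values at 88 df:

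- t, two-sided .05: 1.987
- square root of F(1, 88): 1.987
- Tukey for two groups, q(2, 88)/√2: 1.987

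The three are the same test, applied to one outcome at a time. A simulation (45 per arm, null change scores, 40,000 runs) behaves accordingly: with four outcomes correlated .5, at least one false positive occurs in 15.8% of runs with or without the F-then-Tukey sequence. Planned comparisons limit how many tests are run but do not change the alpha of each.

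**Step 3: chance of at least one false positive.** Assume k tests, each at |z| > 1.96, with common correlation r. At r = 0 this is 1 − .95^k; for k = 4 that is 1 − .8145 = .185. For r > 0 it was found by numerical integration.

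| k | Basis for k | r = 0 | r = .3 | r = .5 | r = .8 |
|---|---|---|---|---|---|
| 2 | mood and sleep | .098 | .095 | .091 | .078 |
| 4 | outcome types named in the global text | .185 | .174 | .156 | .114 |
| 6 | 3 metabolites × 2 regions, if left uncorrected | .265 | .241 | .207 | .139 |
| 8 | illustrative | .337 | .300 | .250 | .157 |
| 12 | illustrative | .460 | .397 | .319 | .186 |

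The k = 4 row applies even if each type were held at .05 internally. With Bonferroni (.05/k) every cell is at or below .049.

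**Step 4: the primary labels side by side.**

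| Place | What is called primary |
|---|---|
| Lay Summary | PTSD symptoms; brain structure, function, connectivity; neurochemistry |
| Global Statistical Analysis Approach | mood and sleep |
| Power Analysis | several hypotheses, unlisted |
| MRS Analyses | Glu, GABA, NAA |

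The first two rows do not overlap: sleep and mood are absent from the Lay Summary's list, and PTSD symptoms are absent from the global text's primary analyses. Aim 4 (referring to Aim 1) and the ROI text on the masked affect task also use the word, but may mean primary within that aim or task.

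**Step 5: the task-fMRI rules side by side.**

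| | Global text | FMRI Statistical Analysis |
|---|---|---|
| ROI / small volume | FWE | FDR |
| Whole brain | FDR | FWE |

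The two are reversed. The FDR rule for resting-state connectivity covers a different analysis and is not part of this conflict.

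**The case against.** The strongest reply is that the plan is underspecified rather than wrong. It never promises family-wise control over every outcome. It names Bonferroni, and the MRS text refers back to the general approach and can be read as extending corrections to all analyses. This stands in part: a conscientious analyst could apply Bonferroni. But nothing says to which planned tests or over how many, so no error rate follows from the text.

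Tukey might also be run over the four arm-by-session cells, with critical value 2.62 instead of 1.987, and measures taken several times a day could have an omnibus F with more than 1 df. Both are fair. Either could give some protection within an outcome or outcome type, but none between types. The simulation likewise compares identical tests by construction; the argument rests on the equal critical values.

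The metabolite label may mean primary within spectroscopy only. That is reasonable but changes little, because the Lay Summary already counts neurochemistry as a primary outcome and conflicts with mood and sleep.

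The fMRI-specific rules might be taken to override the global summary, and the whole-brain analyses are called exploratory. The plan does not state any order of precedence, so the ROI conflict in particular remains.

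Finally, the registry entry may name a primary outcome. It lies outside these documents and cannot settle what they say.

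**Conclusion.** The concern holds and should be resolved before unblinded analysis. The stated control of Type I error does not operate across outcomes, no single primary outcome or listed family exists in these documents, and two stated correction rules for task fMRI contradict each other.

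The size is illustrative because the plan gives neither a success rule nor a test count. If any one unadjusted result at .05 were taken as success, the error would be about 8–10% for two tests, 11–19% for four and 14–26% for six, over correlations of .8 down to 0. The counts of two and four come directly from the global text; six also requires that the MRS corrections are not applied; eight and twelve have no anchor in the text. That the control fails across outcomes does not depend on which count is used. The plan's power figures are not in error; they describe one test.

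**What to change.** Before unblinded analysis:

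1. Name one primary outcome at two-sided .05, or one listed primary family under Holm or Bonferroni. Which outcome (sleep, mood, PTSD symptoms, imaging or MRS) is the sponsor's choice. Use the word primary to match in Aim 4, the Lay Summary, the global analysis text, Power Analysis, ROI Analyses and MRS Analyses.
2. List the remaining confirmatory outcomes as one family under Holm or Bonferroni, in place of reliance on protected F and Tukey across outcomes. If a single study-wide .05 is intended, test this family only after the primary succeeds (every member, if the primary is a family). Other valid schemes exist; what matters is that one is stated.
3. Label every other outcome secondary or exploratory. That includes imaging and MRS only if the sponsor does not choose them above.
4. State one ROI rule and one whole-brain rule for task fMRI, identically in the global text and the fMRI text, and say that the resting-state FDR rule is separate.

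The cost is wording, with no new data, plus some power for outcomes in an adjusted family. Interaction power at f = .25 and N = 90, by assumed pre-post correlation:

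| Alpha | ρ = .5 | ρ = .3 | ρ = 0 |
|---|---|---|---|
| .05 | .997 | .978 | .913 |
| .05/4 | .985 | .925 | .787 |
| .05/6 | .978 | .902 | .742 |
| .05/12 | .961 | .853 | .659 |

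Holm loses no more than this, and a single primary outcome loses nothing.
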